9.2 Study Monitoring

This study is considered moderate risk for monitoring purposes. Protocol and regulatory compliance, including essential regulatory documentation, will be assessed as well as the accuracy and completeness of data points related to the primary study objective semi-annually. If the study design has strata, accrual will be tracked continuously. The first two enrollees and then 10 % of participants will be monitored semi-annually.

The PI and study team are responsible for protocol and regulatory compliance, and for data accuracy and completeness. The study team will meet at appropriate intervals to review case histories or quality summaries on participants and retain copies of the minutes which are signed by the PI.

Clinical Trials Operations (CTO) will verify informed consent documentation of and eligibility status for 50% of trial participants within 5 days of enrollment. Additionally, a quality review will be performed by CTO personnel on 100% of St. Jude participants' informed consent forms to assure completeness.

Overall study conduct, compliance with primary objectives, age of majority consenting, safety assessments and reporting, and the timeliness and accuracy of database entries are monitored routinely. Study documents routinely monitored on selected participants include medical records, database entries, study worksheets, and case report forms. Study documents are monitored for participant status, demographics, staging, subgroup assignment, treatments, investigational drug accountability, evaluations, responses, participant protocol status, off-study and off-therapy criteria, and for all other specifics as detailed in a separate study-specific monitoring plan. The study-specific monitoring plan may be revised over time, to adapt monitoring frequency and/ or intensity to a changing environment when appropriate (for example: new safety signals; positive history of compliance; all participants are in long term follow-up; or the enrollment period has ended).

The recording and reporting of Adverse Events, Serious Adverse Events (SAEs), and Unanticipated Problems (UPs) to include type, grade, attribution, duration, timeliness and appropriateness will be reviewed by the Monitor/ CRM. The CRM will generate a formal report which is shared with the Principal Investigator (PI), study team and the Internal Monitoring Committee (IMC).

Continuing reviews by the Institutional Review Board (IRB) and Scientific Review Committee (CT-SRC) will occur at least annually. In addition, unanticipated problems are reviewed in a timely manner by the IRB.

9.3 Confidentiality

Research Identification numbers will be used in place of an identifier such as a medical record number. No research participant names will be recorded on the data collection forms. The list containing the study number and the medical record number will be maintained in a locked file and will be destroyed after all data have been analyzed.

The medical records of study participants may be reviewed by the St. Jude IRB, FDA, and clinical research monitors.

10.0 STATISTICAL CONSIDERATIONS

10.1 Sample size and accrual

It is logistically realistic and statistically sound (see below) to randomize 160 patients (80/arm) to the intensive or the standard antihypertensive arms. Patients who are randomized but drop out due to reasons as defined in Sections 7.1 and 7.2 before ON is observed or before the reinduction 2 MRI, are considered as inevaluable for the primary endpoint, and should be replaced. Based on past experience, we anticipate ~60 eligible patients to be randomized annually. Conservatively postulating a 12% drop out rate, we need to randomize 180 patients altogether. We thus anticipate a full accrual within 3.5 years.

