6.3 Missed Doses

For the planned analyses, patients within targeted blood pressure ranges (or below target without the use of any antihypertensives) at least 80% of the time will be considered as part of the per-protocol analysis. All patients will be evaluated in the intention to treat analysis regardless of the blood pressure range achieved or number of doses of antihypertensives given as long as imaging to assess osteonecrosis is available.

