7.2 Off-Therapy Criteria

- Completion of prescribed therapy duration (completion of week 19 dexamethasone).
- Discontinuation of TOT17 therapy
- Treatment with high-risk arm therapy (i.e. chimeric antigen receptor T-cell therapy, Reintensification, or transplant)
- Development of unacceptable toxicity during treatment
- Refusal of therapy
- A research participant may also be taken off treatment or off of the study at the discretion of the study PI if persistent non-adherence with protocol directed therapy is documented.

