10.4 Primary Objective

To compare the frequency of radiographically significant osteonecrosis in patients receiving intensive compared to conventional antihypertensive therapy.

The primary endpoint is the number of major joints (hips and knees) with extensive epiphyseal osteonecrosis ($\geq 30\%$ affected surface^{12,13,17}) on MRI after approximately 9 months of chemotherapy (during reinduction 2). All randomized patients with appropriate imaging are considered evaluable and all analyses will be done according to intent-to-treat.

A chart review of 140 TOTXVI patients meeting the eligibility criteria of this study showed the following distribution of the number of affected joints in the low BP within-target group vs. the above-target group:

	Number of affected joints					Total
	0	1	2	3	4	
Above-target (proportion, n)	0.583, 70	0.083, 10	0.233, 28	0.017, 2	0.083, 10	120
Within-target (proportion, n)	0.80, 16	0.05, 1	0.10, 2	0.00, 0	0.05, 1	20

Clearly in each BP group the distribution is bi-modal with local modes at 0 and 2.

The primary analysis will consist of two parts. In the first part the distribution of the number of affected joints will be compared by the exact one-sided Chi-square test comparing the probability of having at least 1 affected joint. Let $P_0(k)$ and $P_1(k)$ be the probability of k affected joints among patients above- and within-target respectively ($k=0,1,2,3,4$). We have noted in the preliminary data that the BP of 14.6% of the eligible patients was within target without any treatment. Therefore, the distribution of the number of affected joints in the control group is anticipated to be $PC(k)=0.854*P_0(k)+0.146*P_1(k)$, and the distribution in the treatment group is anticipated to be $PT(k)=P_1(k)$, $k=0,1,2,3,4$. Applying the preliminary data displayed above to this model, we obtain the anticipated distribution in the control and treatment group as follows:

	Number of affected joints k	
	0	1+
Control	0.615	0.385
Treatment	0.8	0.2

With $n=80$ subjects per group, the one-sided test has the exact power of 78.7% to detect the above anticipated difference at the 5% significance level. The power is calculated using Cytel Studio II.

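### Section 10.1, read literally, makes patients who stop only the blood pressure intervention inevaluable and replaces them even if they are imaged, while Sections 6.3 and 10.4 keep them in the intent-to-treat analysis

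*Combined protocol and SAP*

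**What the plan says.** Two tests for who counts in the primary analysis stand in the current text.

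- **By reason and timing of drop-out.** Section 10.1 covers "Patients who are randomized but drop out due to reasons as defined in Sections 7.1 and 7.2" and says that such patients, "before ON is observed or before the reinduction 2 MRI, are considered as inevaluable for the primary endpoint, and should be replaced".
- **By imaging.** Section 10.4 says: "All randomized patients with appropriate imaging are considered evaluable and all analyses will be done according to intent-to-treat". Section 6.3 puts all patients in the intention-to-treat analysis "regardless of the blood pressure range achieved or number of doses of antihypertensives given as long as imaging to assess osteonecrosis is available", and handles adherence through a separate per-protocol analysis.

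Section 7.1 lists reasons for leaving the study. Section 7.2 lists reasons for coming off therapy, among them "Development of unacceptable toxicity during treatment" and "Refusal of therapy". It adds that a participant may be "taken off treatment or off of the study at the discretion of the study PI if persistent non-adherence with protocol directed therapy is documented". Discontinuation of TOT17 is a separate item on that list. Section 5.3 states that the Reinduction II MRI is done as TOT17 prescribes. Section 10.2 makes the trial open-label.

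**The concern.** Because 10.1 cites the off-therapy list as well as the off-study list, its wording reaches patients who have stopped antihypertensive treatment under the study but have not left TOT17. Their endpoint MRI can still be done. They are out under 10.1 and in under 6.3 and 10.4.

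Toxicity, refusal and non-adherence arise after randomisation and may differ between arms with different pressure targets. Arm assignment is known, and removal for non-adherence is at the study PI's discretion. Dropping these patients would undo part of the protection that randomisation gives the primary comparison. Blinded reading of the MRI does not help, because the selection happens before the film is read.

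There is also a smaller ambiguity. Section 10.1 refers to the time before osteonecrosis is observed as well as the time before the MRI, but 10.4 defines the endpoint on the Reinduction 2 MRI alone. Section 5.3 records MRIs done at other times for symptoms. The plan does not say how a patient with osteonecrosis imaged early but no Reinduction II MRI is handled.

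**Working it through.** **1. The texts side by side, for a randomised patient who goes off therapy before the Reinduction II MRI**

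| Patient | 10.1, literal | 6.3 and 10.4 |
|---|---|---|
| Stops intervention, no MRI | inevaluable, replaced | not evaluable |
| Stops intervention, stays on TOT17, has MRI | inevaluable, replaced | evaluable, analysed as randomised |

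Only the second row conflicts.

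**2. The plan's own power**

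Inputs from 10.4: 80 per arm; one-sided 5%; at least one affected joint in 38.5% (control) and 20% (treatment). Control rate: 1 − (0.854 × 0.583 + 0.146 × 0.80) = 0.385. Full enumeration of the one-sided Fisher exact test gives 78.7%, the stated figure. With 38.5% in both arms the test rejects 3.4% of the time.

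**3. Possible shift in the estimate**

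The fraction f of the intensive arm that stops but is imaged is assumed; the documents do not give it. For these patients' risk I take the plan's above-target rate, (10 + 28 + 2 + 10)/120 = 41.7%. Those who continue have 20%. Then

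intent-to-treat rate = (1 − f) × 0.20 + f × 0.417, and effect = 0.385 − that rate.

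| f (assumed) | Intensive rate | Effect, included | Effect, excluded | Power, included, 80/arm |
|---|---|---|---|---|
| 2% | 20.4% | 18.1 points | 18.5 | 76.6% |
| 4% | 20.9% | 17.6 points | 18.5 | 74.5% |
| 12% | 22.6% | 15.9 points | 18.5 | 65.4% |

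Inclusion moves the arm's rate by f × (stoppers' risk − continuers' risk). The sign therefore depends on the stoppers' risk, and the same formula applies to the control arm with the opposite effect on the difference.

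**4. Behaviour when there is no true effect**

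True rate 38.5% in both arms, 80 analysed per arm. With a fraction f excluded at risk d, the analysed rate is (0.385 − f × d)/(1 − f). Exclusions of 4%, 6% or 8% (intensive) against 2% (control) are assumed; d runs over the plan's range, 20% to 41.7%.

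- 8% against 2%, d = 20%: intensive (0.385 − 0.016)/0.92 = 40.1%, control (0.385 − 0.004)/0.98 = 38.9%. This is 1.2 points against the intensive arm; rejection 2.3%.
- 8% against 2%, d = 41.7%: 38.2% and 38.4%. This is 0.2 points in favour of the intensive arm; rejection 3.6%.
- The 4% and 6% cases lie between these.

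Rejection is thus 2.3% to 3.6%, against 3.4% with no exclusion, and below the nominal 5% throughout.

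**The case against.** The strongest reply is that the literal reading is not the natural one. The sentence sits in the accrual section and serves the 12% inflation. Sections 7.1 and 7.2 also list ordinary completion of evaluations and of therapy, so being on those lists cannot by itself mean having dropped out. On that view a patient who stops the drugs and has the scheduled MRI has not dropped out before it, and 10.1 agrees with 6.3 and 10.4, which already state the analysis set. The group is also narrow: death, loss to follow-up, TOT17 discontinuation and high-risk arm therapy may leave no Reinduction II MRI, and Section 4.1 answers toxicity from a current drug first with a change of therapy.

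The accrual reading is possible and may be what was meant. But 10.1 does not state it, cites the off-therapy list, and rules on evaluability for the primary endpoint as well as on replacement. The narrowness stands and limits the size of the problem.

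Four stronger inferences are tempting, and the documents do not support them:

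- *The plan abandons intent-to-treat.* It does not; 6.3 and 10.4 state it, and 10.1 is the passage out of line.
- *The false-positive rate is inflated.* At the plan's own risks it stays below 5% in every case examined.
- *12% caps the affected share of an arm.* It is a trial-wide rate: 0.12 × 180 = 21.6 patients, which would be 24% of 90 if all fell in one arm. Under the accrual reading it may not count imaged stoppers at all.
- *The lower power figures measure harm from the conflict.* They are the price of the intent-to-treat rule that the plan already adopts.

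The ambiguity about osteonecrosis seen early is secondary. The general references to imaging in 6.3 and 10.4 could cover earlier scans, so it calls for clarification and does not prove the main point.

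**Conclusion.** The point holds as a conflict between rules. Section 10.1 as written excludes and replaces imaged patients who stopped only the blood pressure intervention, and 6.3 and 10.4 keep them. Following 10.1 would create open-label, post-randomisation exclusions that may differ by arm and could move the estimate either way. The actual size is not estimable: the documents give neither the number of such patients by arm nor their osteonecrosis risk. The shift of 0.4 to 2.6 points in the illustration (18.5 less 18.1 to 15.9) rests on assumed fractions confined to the intensive arm and on stoppers carrying the above-target risk. It should be corrected before analysis, when the choice can still be made without knowledge of results.

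**What to change.** Amend Section 10.1 to say that:

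- only randomised patients without evaluable imaging for the primary endpoint are inevaluable and replaced;
- any randomised patient with the Reinduction II MRI is analysed in the assigned arm, whatever their Section 7.2 status, as 6.3 and 10.4 already provide.

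As a secondary clarification, reconcile the reference to osteonecrosis being observed with the 10.4 endpoint: state how a patient imaged earlier but without the Reinduction II MRI is handled, so that evaluability does not depend on the outcome. Leave adherence to the per-protocol analysis in 6.3.

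The cost is one or two sentences for the main change and a short clarification. No procedure is added, because the MRI is already part of TOT17. If imaged stoppers lose benefit, power falls below 78.7% as tabulated above, so keep 180 as the number randomised. With 90 per arm, 2% imaged stoppers and 10% without MRI leave 81 per arm and 76.7% power; 4% and 8% leave 83 and 75.7%; 12% and none leave 90 and 69.9%. These splits are assumed, with the stopper share rescaled to those imaged.

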10.2 Randomization

Open-label, stratified block randomization with block size of 4³⁹. Randomization will be stratified by site (SJCRH and other), gender, self-declared race/ancestry (White Non-Hispanic and other) and hypertension requiring >1 dose of medication before Day 4 (Yes/No).

Analyses for the primary and secondary objectives will not be stratified. If it is determined that certain important factors are not balanced between the two treatment arms, appropriate regression models (such as logistic or integer response models) will be applied. The power assessment below is based on an unstratified Chi-square test.

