Brief Outline of Treatment Plan: Patients will be randomized on day 4 of induction therapy to either conventional or intensive blood pressure goals. Patients will be treated with the long-acting antihypertensive lisinopril to achieve blood pressure control as indicated by their randomized arm. Long-acting therapy will be adjusted every 3-4 days as needed to achieve targeted control based on the median of blood pressures obtained in that period. Treatment of hypertension to the target will continue until the completion of reinduction II therapy. Patients will be evaluated for osteonecrosis as indicated in their primary therapeutic protocol using MRI during reinduction II.
Study Design: Randomized unblinded trial of conventional vs. intensive hypertensive control. Evaluation of the MRIs defining the primary endpoint will be performed by a blinded radiologist.
Sample Size: We will randomize 160 evaluable patients (180 total).
Data Management: Data management and statistical analysis will be provided locally by the Comprehensive Cancer Center Hematological Malignancies Program and the Biostatistics Department at St. Jude Children’s Research Hospital.
Human Subjects: The risks to subject will be related to the toxicity of antihypertensive therapy. Side effects are anticipated to be mild and limited to reversible orthostatic/postural hypotension and transient increases in creatinine. Patients will be informed of this and other minor side effects during informed consent discussion. Adverse events will be monitored and reported and treated appropriately.

TABLE OF CONTENTS

1.0	OBJECTIVES	1
1.1	Primary Objective	1
1.2	Secondary Objectives	1
1.3	Exploratory Objectives	1
2.0	BACKGROUND AND RATIONALE	2
2.1	Background	2
2.2	Rationale	2
2.3	Background and Rationale for Ancillary and Exploratory Studies	3
3.0	RESEARCH PARTICIPANT ELIGIBILITY CRITERIA AND ENROLLMENT	4
3.1	Inclusion Criteria	4
3.2	Exclusion Criteria	4
3.3	Research Participant Recruitment and Screening	5
3.4	Enrollment on Study at St. Jude	5
3.5	Enrollment Instructions for Collaborating Sites	5
4.0	TREATMENT PLAN	6
4.1	Treatment	6
4.2	Participation of St. Jude Affiliates in the Treatment Plan	9
4.3	Treatment Modifications for Collaborating Sites	9
4.4	Supportive Care	9
4.5	Symptom Survey and Semi-structured Interviews	10
5.0	REQUIRED EVALUATIONS, TESTS, AND OBSERVATIONS	12
5.1	Pre-Study Evaluations	12
5.2	Evaluations during Therapy	12
5.3	Response Evaluations	13
5.4	Off-Study Evaluations	13

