3.4 Enrollment on Study at St. Jude

A member of the study team will confirm potential participant eligibility and complete all sections of the Participant Eligibility checklist, print, and sign. If the enrollment will be entered by Clinical Trials Operations (CTO), then the study team must send the completed checklist to CTO by email [REDACTED] or fax [REDACTED] [REDACTED] (follow fax by a phone call to [REDACTED] to ensure receipt).

The Study Team or CTO will enter the Eligibility checklist information into the central enrollment system and release an informed consent form. The study team will provide a copy of the study informed consent form (ICF) to the participant family for their consideration and reference. The entire signed ICF must be forwarded to CTO: [REDACTED] or faxed [REDACTED] so that the enrollment will show in the protocol Milli tab and for study-specific orders to be generated in Milli.

To assist with enrollments and consent release, the CTO staff is available during office hours. After hours, weekends, and holiday patient enrollment issues please call the St. Jude study coordinator or refer to the CTO intranet site for additional resources and instructions: [REDACTED].

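### A single published block size of 4 in an open-label trial makes part of the allocation sequence predictable, realistically at St. Jude, and selective enrolment there is possible

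*Combined protocol and SAP*

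**What the plan says.** - The Protocol Summary describes the study as a "Randomized unblinded trial of conventional vs. intensive hypertensive control".
- Section 10.2 specifies an open-label design with "stratified block randomization with block size of" 4. One size is given, with no mention of varying it or of withholding it from investigators.
- Section 10.2 also lists the factors: "Randomization will be stratified by site (SJCRH and other), gender, self-declared race/ancestry (White Non-Hispanic and other) and hypertension requiring >1 dose of medication", the last of these counted up to Day 4. Four two-level factors make 16 strata, 8 of them belonging to SJCRH alone.
- Section 10.1 plans "to randomize 160 patients (80/arm) to the intensive or the standard antihypertensive arms", which implies 1:1 allocation and so two places per arm in each block. With dropout, 180 patients are to be randomised.
- Section 3.4 covers enrolment at St. Jude: "A member of the study team will confirm potential participant eligibility and complete all sections of the Participant Eligibility checklist". On data entry it adds: "The Study Team or CTO will enter the Eligibility checklist information into the central enrollment system".
- Section 3.5 differs for collaborating sites. The site completes the checklist, but Clinical Trials Operations (CTO) makes the entry.
- The Protocol Summary and Sections 5.3 and 6.1 provide for MRI reading by a radiologist blinded to arm.

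**The concern.** In an unblinded trial each past allocation is visible to those who treat the patient. If the block size is known and never changes, a team that keeps count within a stratum knows some future allocations before the patient is enrolled. The last place in every block is certain, and the third is certain whenever the first two went to the same arm. All four stratification factors are known before randomisation, so the team also knows which list a patient would draw from.

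What is at stake is who enters each arm. A team that knows the next arm could decide whether to approach or enrol a particular patient. The blinded MRI read protects the assessment of the outcome but comes after that decision. Section 10.2 leaves the primary analysis unstratified and brings in regression only if important factors turn out unbalanced. That cannot correct for selection on something not recorded.

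**Working it through.** The plan gives no figure for predictability, so there is none to reproduce. The inputs are block size 4 (10.2), 1:1 allocation (from 80 per arm, 10.1), 180 randomised (10.1) and 16 strata, 8 of them at SJCRH (10.2). Two inputs are assumptions: an even spread over strata, and the number enrolled at SJCRH, which the documents do not give.

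**Certain allocations, completed blocks.** There are 6 equally likely sequences in a 1:1 block of 4. The chance that the next arm is certain is 0, 0, 1/3 and 1 at positions 1 to 4. The share is (0 + 0 + 1/3 + 1)/4 = 33.3%.

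**Best guess, completed blocks.** Guessing the arm with more places left is right with probability 1/2, 2/3, 2/3 and 1 at the four positions. At position 3 this is 1/3 × 1 + 2/3 × 1/2 = 2/3. The sum is 2.833 of 4, or 70.8%, against 50% by chance.

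**Allowing for unfinished blocks.** If the last block stops after 0, 1, 2 or 3 patients, the certain allocations fall short of one third of the stratum by 0, 1/3, 2/3 and 2/3, an average of 5/12. With 180/16 = 11.25 patients per stratum, the expected number certain is 11.25/3 − 5/12 = 3.33 per stratum. Over 16 strata that is about 53 of 180, or 29.6%. Simulation gives the same figure.

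**SJCRH alone (8 strata).** The expected number certain is N/3 − 8 × 5/12 = N/3 − 3.33:

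| Patients at SJCRH (assumed) | Certain allocations | Share at SJCRH |
|---|---|---|
| 60 | 16.7 | 27.8% |
| 90 | 26.7 | 29.6% |
| 120 | 36.7 | 30.6% |

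**Effect of varying the block size.** These figures are for an observer who sees the whole stratum history and knows which sizes are possible. Mixed sizes were simulated.

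| Block sizes | Certain allocations | Best guess correct |
|---|---|---|
| 4 only, completed blocks | 33.3% | 70.8% |
| 4 or 6 | about 6% | about 68% |
| 4, 6 or 8 | 2–3% | about 67% |

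**Balance.** With blocks of 4, the imbalance left in a stratum has variance 0, 1, 4/3 or 1 after 0, 1, 2 or 3 patients in the last block, an average of 0.833. Over 16 strata the standard deviation is √(16 × 0.833) = 3.65, and the mean absolute difference between arms is about 0.80 × 3.65, close to 3 patients of 180. Simulation with mixed sizes gives about 3.2 to 3.4, moving by a tenth or so between runs.

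**The case against.** Several counter-arguments carry weight.

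- **Scope.** A reader might infer that one third of all allocations in the trial are known to whoever enrols. The documents do not support that. The figure needs completed blocks and sight of the whole stratum sequence. In the 8 non-SJCRH strata several sites share each list and CTO makes the entries, so one site cannot rebuild the sequence from its own patients. This stands and limits the point mainly to SJCRH.
- **Delay.** Randomisation is on Day 4 and Section 3.1 excludes anyone beyond 4 days of therapy. At 60 patients a year over 16 equal strata, one patient arrives per stratum every 365/(60/16) = 97 days. Assuming random arrivals, the chance of a second within 4 days is 1 − exp(−4/97), about 4%. Swapping two patients is rarely feasible. What remains is not approaching or not enrolling a patient.
- **Existing checks.** The exclusions are mostly documentable, and under Section 9.2 CTO verifies eligibility and consent for 50% of participants within 5 days. That check sees enrolled patients only, not those never approached. Section 3.3, on recruitment and screening, was not available for this review, so no safeguard there can be called absent.
- **Size of bias.** A reader might combine the chart-review rates in Section 10.4 (50/120 = 41.7% above target, 20% within target) with some rate of steering to get a bias in percentage points. Those rates are by achieved blood pressure, not by a characteristic shown to be known at enrolment, and the documents give no steering rate. The nearest early marker, medication before Day 4, is already a stratification factor. No such estimate is supportable.
- **Modest gain.** Varying the block size lowers best-guess success by only a few points. This is true; the benefit lies in removing certainty.

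**Conclusion.** The point holds as a limited weakness in allocation concealment. With a fixed, published block of 4, about 30% of allocations are certain to someone who follows a stratum. That is realistic mainly at SJCRH, where it would mean roughly 17 to 37 patients if 60 to 120 are enrolled there. That range rests on an assumed SJCRH share, an even spread over strata and a team that tracks earlier allocations.

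The documents show opportunity, not conduct. They do not support a statement that enrolment has been steered, or that the primary comparison is biased by any stated amount. The change is still worth making, because selection at entry cannot be repaired in the analysis and the remedy is cheap.

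**What to change.** In Section 10.2, replace the fixed size of 4 with permuted blocks of randomly varying size, generated and held by Biostatistics. State that the sizes are kept in a restricted randomisation document and are not disclosed to the study team or sites. The cover page shows activation on 08-28-2020, so this needs an amendment that applies to the unused part of each stratum's list. The amendment should also say how the open block in each stratum is handled: finishing it leaves its last places predictable, while abandoning it adds a little imbalance.

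The cost is the amendment, a new list, and a rise in expected arm imbalance from about 3.0 to about 3.2–3.4 patients of 180. Sizes 4 and 6 keep balance slightly better; adding 8 removes more of the certainty.
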